4.2 Analysis of variables

4.2.1 Disposition of subjects

Subject dispositions (number and percentage of subjects enrolled, subjects randomized, subjects who received at least one dose of study treatment, subjects who completed the treatment and subjects who completed the study) will be presented in a summary table for each treatment group and overall (two different totals will be considered as following: one with placebo and one without placebo subjects). Subject disposition related to the global/country situation will be presented in the same summary table at final analysis only. A listing including all standardized disposition terms will be also provided for all discontinued subjects. Both, the table and the listing will be based on all enrolled subjects population. The table will be performed in IDMC reports and at final analysis. The listing will be provided at final analysis.

The number of subjects belonging to each analysis population will be presented in a separate summary table for each treatment group. The table will be based on all randomized subjects population and will be performed at final analysis. Listings of all subjects excluded from each analysis population will be also provided at final analysis. The listings will include reason for exclusion from respective population and will be based on all enrolled subjects population.

Randomization code and actual kit will also be listed at final analysis.

4.2.2 Important protocol deviations

The number and percentage of subjects with at least one Important protocol deviation (IPD) will be displayed following the Protocol Deviation Management Plan categories for each treatment group and overall (including sub selection related to the global/country situation; additionally two different totals will be considered as following: one with placebo and one without placebo subjects), for all subjects in the as-treated population.

IPDs will be presented in IDMC reports and at final analysis. The listing will be presented for final analysis.

Subjects meeting an IPD category more than once will be counted once for the corresponding IPD category. Any subjects who have more than one IPD category will be counted once in the overall summary.

4.2.3 Baseline assessment and other subject-specific characteristics

4.2.3.1 Demographic and subject-specific characteristics

All demographic and subject-specific characteristics reported in section [3.2.1](#) will be presented in summary tables for each treatment group and overall (two different totals will be considered as following: one with placebo and one without placebo subjects); Age, height, weight and BMI will be summarized descriptively as continuous variable with n, mean, median, SD, minimum, and maximum; all the other demographic and subject-specific characteristics will be summarized as categorical variables with the number and percentages of subjects by categories. Age group categories $\geq 21 - < 40$; $\geq 40 - < 50$; $\geq 50 - < 65$; ≥ 65 will be summarized. Only the baseline measurement for height, weight and BMI will be considered.

All demographic and subject-specific characteristics will be also provided in listing on the ITT population for final analysis only.

The tables will be based on the ITT population and will be presented in IDMC reports and at final analysis.

Indication (NSTEMI, STEMI), type of coronary procedure (Diagnostic coronary angiography only, Coronary intervention/revascularisation), extent of disease at start of angiography, procedure type (PCI, CABG, No procedure), stent (yes, no) and type of stent will also be summarized descriptively as categorical variables. The table will be based on the ITT population and will be provided for final analysis. Listings will be provided based on the ITT population for final analysis only.

4.2.3.2 Medical history

Relevant and disease related medical history, cardiac history and risk factor as described in section [3.2.2](#) will be presented in summary tables as number and percentages of subjects by System Organ Class (SOC) and Preferred Term (PT) for each treatment group and overall (two different totals will be considered as following: one with placebo and one without placebo subjects). Subjects with multiple events in the same SOC/PT will be counted only once in that SOC/PT. Subjects with events in more than one SOC/PT will be counted once in each of those SOC/PT. Table will be sorted alphabetically by SOC and PT. The table will be based on the ITT population and presented at final analysis only.

4.2.4 Concomitant medications

Concomitant medications are defined in section [3.5](#). The number and percentage of subjects with at least one concomitant medication and the number and percentage of subjects by ATC level 4 and product name will be provided using the ITT population at final analysis only.

Additionally, the number and percentage of subjects with at least one cardiac medication will be presented using the ITT population at final analysis only. Cardiac medications include the following ATC level 2 classifications: antithrombotic agents, agents acting on the renin-angiotensin system, beta blocking agents, drugs used in diabetes, and lipid modifying agents. Only medications started prior to randomization or ongoing at the end of study will be summarized.

Cardiac concomitant medication started prior to randomization is defined as any medication with a start date prior to randomization date.

Cardiac concomitant medication ongoing at end of study is defined as any medication with a start date prior to or on the date of end of study or ongoing or no end date.

Concomitant medications will be listed for the ITT population at final analysis.

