3.1.1.3 Imputation of adverse event / concomitant medication stop date

Missing stop dates (where in eCRF UN, UNK and 0000 indicate unknown or missing Day, Month and Year respectively for partial missing dates, while completely missing dates would be left empty):

- Completely missing dates will not be imputed.

Partial missing AE/CM end dates are imputed as below:

- If the AE/CM is not ongoing and if only the day is missing: Assume the last day of the collected month.
- If the AE/CM is not ongoing and the month is missing: Assume 31-DEC-YYYY (of the collected year).

After applying these rules, if the imputed AE or concomitant medication (CM) stop date is after the date of death (or after the date of the end of the study), the imputed stop date will be the same as the date of death (or the date of the end of the study).

- If the AE/CM is ongoing, the stop date will remain missing. Completely missing dates will not be imputed.

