3.5 Concomitant medications

The most up to date version of WHO Drug Dictionary (WHO-DD) is used to classify medications by World Health Organization (WHO) Anatomical Therapeutic Chemical (ATC) classification of ingredients.

The imputation method described in section [3.1.1.2](#) and [3.1.1.3](#) is used in case of medication start date or stop date partially missing. Completely missing concomitant medication start dates and stop dates are not imputed.

After the end date imputation, the medications will be classified as either prior or concomitant (but not both) according to its stop date. Concomitant medication is defined as any medication with a stop date on or after the first dose of study drug, or any medication taken prior to study

drug and that is ongoing. Medications with completely missing stop date are classified as concomitant.

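### SAP 4.2.4 counts a cardiac medication as ongoing at end of study on its start date alone, so drugs stopped on study are reported as ongoing

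*SAP*

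**What the plan says.** SAP 4.2.4 plans, for the ITT population at final analysis, a count of participants with at least one cardiac medication. Cardiac medications are five ATC level 2 classes: "antithrombotic agents, agents acting on the renin-angiotensin system, beta blocking agents, drugs used in diabetes, and lipid modifying agents". The section then restricts the content: "Only medications started prior to randomization or ongoing at the end of study will be summarized".

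It defines both categories:

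- Started before randomization: "Cardiac concomitant medication started prior to randomization is defined as any medication with a start date prior to randomization date".
- Ongoing at end of study: "any medication with a start date prior to or on the date of end of study or ongoing or no end date".

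Two other SAP sections bear on the second definition. Section 3.5, to which 4.2.4 refers for the meaning of concomitant, says "Concomitant medication is defined as any medication with a stop date on or after the first dose of study drug", or one taken before study drug that is ongoing, and adds "Medications with completely missing stop date are classified as concomitant". Section 3.1.1.3 says "If the AE/CM is ongoing, the stop date will remain missing". It also fills partial stop dates of medications that are not ongoing with the last day of the month or 31 December, and cuts them back to the date of death or end of study if they fall later.

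**The concern.** A medication is ongoing at a date if it had started by then and had not stopped. The SAP's definition accepts the first half as sufficient. Almost every medication recorded in a trial has a start date on or before the end of the trial, so the definition separates almost nothing.

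Background therapy is relevant here. Protocol 4.2.2.1 notes that regression of non-calcified plaque volume has been observed with statin use, and that volume in the most diseased segment is the primary endpoint. Protocol 4.1 encourages the highest tolerated statin dose without mandating it, and Protocol 5.1 asks only that lipid-lowering therapy ideally be stable during treatment. On-study changes are possible. A table labelled as therapy ongoing at end of study should not include drugs that participants had already stopped.

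**Working it through.** The documents give no figure to reproduce, so the check applies the rule to records.

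**Rules compared**

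- As written: start ≤ end of study, OR ongoing, OR no stop date.
- A (if *and* was meant for the first *or*): start ≤ end of study AND (ongoing OR no stop date).
- B (if *stop date* was meant for *start date*): stop ≥ end of study, OR ongoing, OR no stop date.

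End of study is set at Day 325, the last visit in Protocol Table 5.

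| Start | Stop | As written | A | B |
|---|---|---|---|---|
| Day -100 | Day 30 | ongoing | no | no |
| Day 40 | Day 60 | ongoing | no | no |
| Day 40 | Day 325 | ongoing | no | ongoing |
| Day -100 | none, flagged ongoing | ongoing | ongoing | ongoing |
| Day 40 | none, not flagged | ongoing | ongoing | ongoing |
| missing | Day 60 | no | no | no |
| missing | none, flagged ongoing | ongoing | no | ongoing |

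The first two rows are the error. The only stopped drug that the written rule leaves out is one whose start date is missing.

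**All complete date pairs.** Take start days -365 to 325 (the lower limit is an assumption and does not affect the result) and stop days 1 to 325, with stop on or after start.

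- Starts from -365 to 1: 367 start days × 325 stop days = 119,275 pairs.
- Starts from 2 to 325: 324 + 323 + … + 1 = 324 × 325 / 2 = 52,650 pairs.
- Total: 119,275 + 52,650 = 171,925 pairs, each with a recorded stop date.

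Classed as ongoing:

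- As written: 171,925 (100%).
- A: 0.
- B: 691 (691 / 171,925 = 0.4%), the pairs that stop on Day 325 itself.

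These are counts of possible date pairs, not expected frequencies in patients. They show only that the written rule does not discriminate.

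**Overlap of the two categories.** Pairs with a start before Day 1: 366 × 325 = 118,950. All 118,950 also meet the written ongoing rule. This follows directly, because a start before randomization is necessarily before end of study.

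**Do other sections repair it?** Section 3.5 makes a medication stopped before first dose prior rather than concomitant. If that carries into 4.2.4, a drug taken from Day -100 to Day -20 drops out. It places no condition on stopping after first dose. Section 3.1.1.3 deals only with filling in dates. Neither requires the drug to be in use at end of study.

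**The case against.** The strongest case on the other side is that this is a drafting slip in a descriptive table. The label makes the intent plain, no model uses the variable, and statin intensity at screening is already a stratification factor, a model covariate (SAP 4.1.1) and a CTA subgroup (SAP 4.2.8.1.5). Start and end dates, dose and frequency are recorded (Protocol 6.5), and SAP 4.2.4 also plans an ATC level 4 table and a listing of concomitant medications. Most of this stands and sets the limit on the impact. It does not make the definition right. The text does not show whether *and* or *stop date* was meant, and rules A and B classify some records differently, so a programmer would have to guess.

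A reader might infer more than the documents support:

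- **That the trial could not detect unequal background therapy between arms.** SAP 4.2.4 gives this table neither a by-arm layout nor that purpose, and stopping can be recovered from the listing.
- **That the rule hides statin dose changes.** Classes are at ATC level 2, so a dose change or a switch within a class would not show at that level under any rule.
- **That every medication ever started is counted.** Section 3.5 classes those stopped before first dose as prior.

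A further fair point concerns layout. If the two categories are combined in one display, a drug started before randomization and stopped early stays in the table even under a corrected rule. Correcting the definition alone would then change only drugs that were both started and stopped after randomization.

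**Conclusion.** The definition is wrong as written. Any cardiac medication with a known start date that was stopped between first dose and end of study is classed as ongoing at end of study. For known start dates, the category of drugs started before randomization lies inside the ongoing category.

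The consequence is limited to one descriptive ITT table. For each class, reported end-of-study use is too high by the proportion of participants who took the class on or after first dose and had stopped it by the end. The documents give no stopping rate, so that proportion cannot be put in figures; it is zero if nobody stops. The ANCOVA, MMRM and Cox results do not change.

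This rests on reading the *or* literally and on no further condition appearing in the table shells, which are not part of the documents reviewed. It merits correction before the table is produced, but it is not a threat to the primary analysis.

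**What to change.** Replace the definition in SAP 4.2.4 with one that has both parts:

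1. the start date is on or before the participant's own end-of-study date, or is completely missing; AND
2. the medication is flagged ongoing, OR has no stop date, OR has a collected stop date on or after that end-of-study date.

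Three details matter:

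- The missing-start allowance is needed because SAP 3.1.1.2 does not impute completely missing start dates. Without it, a long-term drug flagged ongoing but with an unknown start would be lost, as in rule A.
- A partial stop date on a record marked not ongoing should not count as ongoing merely because SAP 3.1.1.3 fills it or cuts it back to end of study.
- The text should say the participant's own date, because Protocol 4.4 defines the end of the study as the last participant's last visit or assessment globally.

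Show drugs started before randomization and drugs ongoing at end of study as separate categories, so that stopping a class becomes visible.

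The cost is one line of SAP text and the matching program code. Reported end-of-study use will be slightly lower than under the present wording.

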4.2.5 Treatment and compliance

4.2.5.1 Exposure

Exposure and extended exposure are described in section [3.4.1](#). Exposure, duration and cumulative exposure over time (days) will be presented in a summary table for each treatment group and overall (total will not include placebo subjects). Summary statistics will include n, mean, SD, 1st and 3rd quartile, median, minimum, and maximum. The same summary will be provided for subjects being dosed with at least 6 doses (it can be non-consecutive). The table will be based on the as-treated population and will be provided in IDMC reports and at final analysis.

Exposure and extended exposure will also be summarized as categorical variables in the as-treated population in IDMC reports and final analysis.

Exposure data will also be reported in a listing for all subjects in the as-treated population for final analysis.

4.2.5.2 Compliance

Considering the way of the treatment administration, compliance to the treatment will not be analysed. Administration of investigational product will be listed for the as-treated population for final analysis.

4.2.5.3 Overdose

Any dose of MEDI6570 greater than the intended maximum investigated dose per subject will be considered an overdose. Overdoses will be reported in a listing for all subjects in the as-treated population for final analysis.

4.2.6 Study Recruitment

The number and percentage of recruited subjects per geographic region, country and centre will be provided for each treatment group and overall using the ITT population in IDMC reports and at final analysis.

4.2.7 Stratification factors

The number and percentage of subjects stratified by geographic region and by statin therapy status at randomization, as explained in sections 4.2.8.1.5, 4.2.8.2.2, 4.2.8.3.2, 4.2.10.1.1 will be provided for each treatment group and overall using the ITT population in IDMC reports and at final analysis.

Randomization scheme and codes including the stratification factors will be listed for all randomized subjects at final analysis.

4.2.8 Primary and secondary efficacy endpoints

All the outputs listed below will be presented in final analysis.

4.2.8.1 CTA analysis

An overview of the ANCOVA analysis (section 4.1.1) performed to compare MEDI6570 [REDACTED] versus placebo, MEDI6570 [REDACTED] CCI [REDACTED] versus placebo MEDI6570 [REDACTED] CCI [REDACTED] versus placebo and pooled MEDI6570 [REDACTED] CCI [REDACTED] doses versus placebo will be presented. This overview will include the difference in LSmeans between treatment groups and placebo from the ANCOVA analysis on change from baseline to Day 253 of each of the following CTA variables (sections 3.3.1 and 3.3.2.3):

- NCPV_{MD}
- Global non-calcified plaque volume
- Low attenuation plaque volume

All parameters assessed by CTA are assumed to be normally distributed.

Baseline and post-baseline definitions are detailed in section 3.1.2.

Tables and listings will be based on the CTA analysis population and presented for each treatment group.

CTA variables will be reported in a listing.

Different subgroup analyses will be performed at final analysis: a complete description of these analyses is provided in section 4.2.8.1.5.

4.2.8.1.1 Primary efficacy endpoint NCPV_{MD}

NCPV_{MD} is described in section 3.3.1. Baseline and post-baseline definitions are detailed in section 3.1.2. Tables and listings will be based on the CTA analysis population and presented for each treatment group.

NCPV_{MD} will be summarized descriptively as continuous variable at Baseline, Day 122 and Day 253 for observed value, change and percent change from baseline. Change of NCPV_{MD} will be also presented in figure with mean and SD by visit.

ANCOVA model described in section 4.1.1 will be used for change from baseline to Day 253 of NCPV_{MD}.

A forest plot will also be presented in figure for the 4 comparisons between active groups and placebo using the ANCOVA model for change of NCPV_{MD} at Day 253.

Sensitivity analyses for the primary endpoint are described in section 4.2.8.1.2.

4.2.8.1.2 Sensitivity analysis of the primary efficacy endpoint

All the tables and figure for analysis of primary efficacy endpoint presented in section 4.2.8.1.1 will be repeated with the aim to consolidate the results obtained with the previous ANCOVA model and with summary statistics.

The following sensitivity analyses will be performed on the per-protocol CTA analysis population:

- The same ANCOVA model (sensitivity analysis 1);
- The same ANCOVA model restricted to those who completed treatment (no missing treatment at Day 253) (sensitivity analysis 2);

The following sensitivity analyses will be performed on the CTA analysis population:

- The same ANCOVA model but without subjects having received both CCI [REDACTED] and CCI [REDACTED] (sensitivity analysis 3);
- The same ANCOVA model restricted to subjects with no scanner change between baseline and Day 253 (sensitivity analysis 4).

4.2.8.1.3 Secondary efficacy endpoints NCPV and LAPV

NCPV and LAPV are described in section 3.3.2.3. Baseline and post-baseline definitions are detailed in section 3.1.2. Tables and listings will be based on the CTA analysis population and presented for each treatment group.

Parameters will be summarized descriptively as continuous variable at Baseline, Day 122 and Day 253 for observed value, change and percent change from baseline. Change from baseline in NCPV and LAPV will be also presented in separate figures with mean and SD by visit.

NCPV and LAPV will follow same distribution of NCPV_{MD}. At this regard, only if NCPV_{MD} after normality checking will be log-normally distributed, both of these parameters will be assumed log-normally distributed.

An ANCOVA model as described in section 4.1.1 for change from baseline in NCPV and LAPV at Day 253 will be also separately presented for each of these CTA variables. Separate forest plots will be also presented in figure for the 4 comparisons between active groups and placebo using the ANCOVA model for change from baseline in NCPV and LAPV at Day 253.

Subgroup analysis as described in section 4.2.8.1.5 will be performed including baseline and Day 253.

Sensitivity analyses for the secondary endpoints NCPV and LAPV are described in section 4.2.8.1.4.

4.2.8.1.4 Sensitivity analysis for NCPV and LAPV

All the tables for analysis of NCPV presented in section 4.2.8.1.3 will be repeated with the aim to consolidate the results obtained with the previous ANCOVA model and with summary statistics.

The following sensitivity analyses will be performed on the per-protocol CTA analysis population:

- The same ANCOVA model (sensitivity analysis 1)
- The same ANCOVA model restricted to those who completed treatment (no missing value at Day 253) (sensitivity analysis 2)

The following sensitivity analysis will be performed on the CTA analysis population:

- The same ANCOVA model restricted to subjects with no scanner change between baseline and Day 253 (sensitivity analysis 3)

4.2.8.1.5 Subgroup Analysis of CTA endpoints

Subgroups planned for analysis include but are not limited to those defined by randomization (by IVRS) stratification factors. Stratification factors include geographic region (Asia, North America, Rest of the World) and statin therapy status (no, low or moderate and high intensity statin therapy).

A complete list of the subgroups ((*subgroup level 1*; *subgroup level 2*; ...; *subgroup level x*) analysed at the final analysis for NCPV_{MD} and NCPV is provided below.

- Sex (*Male; Female*)
- Age (<65 ; ≥ 65 years)
- Race (*Caucasian; Non-Caucasian*)
 - with *Caucasian* = White and *Non-Caucasian* = American Indian or Alaska Native, Asian, Black or African American, Native Hawaiian or Other Pacific Islander, Other.
- Geographic region
 - *Asia, North America; Rest of the World*
 - *Western (North America and Rest of the World); Asia*
Asia will not be repeated in the second subgroup.
- Diabetes mellitus (*Presence; Absence*)
 - with *Presence* = if diabetes mellitus (type 1 or type 2) in Medical History (MH) or Cardiac History and Risk Factor (SPECHIS) forms and *Absence* otherwise.
- Smoking Status (*Smoker; Non-smoker*)
 - with *Smoker* = current or former smoker and *Non-smoker* = never smoked.
- Qualifying MI Type (*STEMI; NSTEMI*)
 - using Indication field from Coronary Revascularisation - Qualifying Event (PROCCA) form
- Baseline eGFR (<60 mL/min/1.73 m²; ≥ 60 mL/min/1.73 m²)
- Statins (*None/Low/Moderate intensity; High intensity*)
- Baseline NT-ProBNP
 - ($<$ Median; \geq Median)
 - ($<$ 125 pg/mL; \geq 125 pg/mL)
- **CCI**
[REDACTED]
- Baseline Global NCPV ($<$ Median; \geq Median) to be performed only for Global NCPV using baseline value computed after segment matching to Day 253
- Baseline NCPV_{MD} ($<$ Median; \geq Median) to be performed only for NCPV_{MD}

using baseline value computed after segment matching to Day 253

- Baseline LDL ($<70 \text{ mg/dL}$; $\geq 70 \text{ mg/dL}$)
- Coronary intervention/revascularisation (for qualifying event) (Yes, No)
using Type of coronary procedure from Coronary Revascularisation - Qualifying Event (PROCRA) form
- Time from the date of qualifying event to randomization ($<3 \text{ months}$; $\geq 3 \text{ months}$)
in case of multiple qualifying events, the latest event is used.
- Baseline LVEF ($<50\%$; $\geq 50\%$)

Subgroup analysis will present both summary and inferential tables (ANCOVA model described in section 4.1.1) for CTA analysis population. ANCOVA model will be presented for change at Day 253 for NCPV_{MD} and NCPV.

